There is no FDA-approved therapy for PRP, not a single published systematic therapeutic clinical trial, and no established guidelines for measuring disease severity. Commonly prescribed systemic medications include acitretin and methotrexate, but these have treatment failure rates of over 40% (1) and can be limited by side effects. Tumor necrosis factor inhibitors have been used for PRP but have even higher failure rates (1). While there are no published reports of IL-23p19 subunit-targeted therapy in PRP, there are case reports and case series of the use of IL-12/IL-23p40 subunit inhibition for PRP in over twenty patients (2, 9-23) with 90% of these showing marked improvement, often only 4 weeks after a single subcutaneous injection. For these reasons, guselkumab is proposed as a therapeutic intervention with potential for improving the lives of PRP patients.

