3. STUDY DESIGN AND ENDPOINTS

3.1. Study Design Overview

This will be an investigator-initiated, open-label pilot study of 15 subjects with moderate-to-severe PRP treated with guselkumab at the FDA-approved dosing for psoriasis for 20 weeks, examining the primary efficacy endpoint of mean decrease in PASI score at week-24. Sustained remission will be assessed at week-36. Biopsies will be obtained before the first injection and at week-4 and week-24. Blood tests will be performed for screening and safety and measuring levels of inflammation at Screening, week-0, week-4, and week-24. The study schedule is outlined in Section 5.4., Table 1.

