3.2.4. Exploratory/Mechanistic Endpoints

- Treatment response, as measured by PASI 50, stratified by the presence or absence of germline CARD14 mutations. Genetic CARD14 gain-of-function mutations were identified in 3 families with familial PRP as well as 12.5% of individuals with sporadic PRP (3). Genetic CARD14 mutations will be measured in study subjects and associated with treatment response to guselkumab. Additionally, de-identified samples will be stored indefinitely for future analysis of genes associated with PRP.
- Normalization of CARD14 epithelial expression at week-24. Despite the fact that not all patients with PRP have genetic CARD14 mutations, immunohistochemical staining of CARD14 in 6 of 6 biopsies from sporadic cases of PRP without germline genetic mutations showed increased expression of CARD14 in the keratinocyte spinous and granular layers of the epidermis (2). CARD14 is thought to act in a synergistic manner with IL-17, activating the transcription factor NF-kB. NF-kB activation was shown *in vitro* to stimulate IL-36gamma, which may induce an amplifying feedback loop from IL-23 to IL-17 and back again (6). Cutaneous biopsies will be obtained from subjects before and 24 weeks after treatment with guselkumab. Inhibition of IL-17 by guselkumab is expected to lead to normalization of CARD14 expression by keratinocytes.
- Normalization of cutaneous gene expression at weeks 4 and 24. Upregulation of Th17 cytokines (IL-17A, IL-17F, IL-22) and pro-inflammatory innate cytokines (TNF, IL-6, IL-12, IL-23, IL-1beta) compared to normal skin were observed in lesional skin from 3 subjects with PRP (5). In order to better understand the inflammatory pathways involved in PRP, lesional and non-lesional biopsies will be obtained from subjects at week-0 prior to the first dose of guselkumab, week-4, and week-24. Cutaneous gene expression of the epidermis and dermis will be analyzed by RNA Sequencing (RNA-Seq and therapeutic response to guselkumab is expected to correlate with normalization of epidermal cytokine levels. De-identified tissue samples will be stored indefinitely for analysis.
- Change in serum cytokine levels at weeks 4 and 24. Serum levels of multiple cytokines have been shown to correlate with disease activity in patients with psoriasis (*30*) but these have not been investigated in patients with PRP. Serum cytokine levels before and after treatment with guselkumab will be analyzed by multiplexed bead-based immunoassay.

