7.2.3. Exploratory Endpoint Analyses

- Sustained remission at week-36, measured by the mean change in PASI score from week-24 to week-36, will be analyzed for statistical significance using a paired, two-tailed Student's t-test.
- Treatment response, as measured by PASI 50, will be stratified by CARD14 germline mutations. The proportion of subjects with a PASI 50 response with and without CARD14 mutations will be reported and compared for statistical significance using an unpaired, two-tailed Student's t-test.
- Epithelial expression of CARD14 will be assessed qualitatively by a trained dermatopathologist who is blinded to the biopsy collection time (before or after therapy).
- The gene expression level from the tissue biopsy, before, 4 weeks, and 24 weeks after treatment, will be analyzed for statistical significance using a pared, two-tailed Student's t-test and also compared with normal and psoriatic skin using a two-tailed, two-sample Student's t-test with unequal variance adjusted for multiple comparisons.
- The cytokine level from serum before, 4 weeks, and 24 weeks after treatment, will be analyzed for statistical significance using a pared, two-tailed Student's t-test and also compared with normal and psoriatic serum using a two-tailed, two-sample Student's t-test with unequal variance adjusted for multiple comparisons.

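### Student's t-test on yes/no PASI 50 response by CARD14 status: with about two carriers expected, its p-value can rest on one subject and come out far too small

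*Combined protocol and SAP*

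**What the plan says.** In section 7.2.3 the PASI 50 response proportions "with and without CARD14 mutations will be reported and compared for statistical significance using an unpaired, two-tailed" Student's t-test. For the gene-expression and serum-cytokine comparisons with normal and psoriatic samples, the same section asks for a "two-sample Student's t-test with unequal variance adjusted for multiple comparisons". No such qualifier is attached to the CARD14 comparison, so I read it as the pooled-variance test.

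Section 3.2.4 cites gain-of-function mutations in "3 families with familial PRP as well as 12.5% of individuals with sporadic PRP". Section 3.1 describes an "open-label pilot study of 15 subjects with moderate-to-severe PRP". The eligibility criteria in sections 4.1 and 4.2 do not exclude familial disease. For this comparison the plan names no exact method, no minimum number of carriers, and no rule for zero variance or zero carriers.

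**The concern.** A t-test on 0/1 data relies on a within-group variance estimate and on an approximately normal difference in means. With one to three subjects in one group, neither can be relied on. If everyone in the larger group responds, the pooled variance is close to zero and one non-responding carrier can produce a very small p-value.

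At stake is the planned significance statement linking genotype to response, which is a named mechanistic endpoint. A p-value of 0.005 resting on one subject could be reported as evidence that carriers respond differently.

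**Working it through.** **Plan's own figure.** The only computed design figures are the power values in section 7.1. For n=10, mean change 8 and SD 8, the two-sided paired t-test (df 9, noncentrality (8/8)×√10 = 3.16) gives 0.8031, as stated. They concern the primary endpoint; none is given for the CARD14 comparison.

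**Inputs.** N=15 (sections 3.1 and 7.1); carrier rate 12.5% (section 3.2.4, sporadic disease). Assumed, because the documents do not give them: a common response rate of 50-95%, and carrier rates of 20% and 25% to represent more familial cases.

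**Number of carriers.** Expected: 15 × 0.125 = 1.875. From Binomial(15, 0.125): P(0)=13%, P(1)=29%, P(2)=29%, P(1 to 3)=76%. At 20% and 25%, the expected counts are 3.0 and 3.75, and P(1 to 3) is 61% and 45%.

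**One table by hand: 1/2 carriers, 13/13 non-carriers respond.**
- Difference in proportions: 1 − 0.5 = 0.5.
- Within-group sum of squares: 2 × 0.5² + 0 = 0.5. Pooled variance: 0.5/13 = 0.0385.
- Standard error: √(0.0385 × (1/2 + 1/13)) = 0.149. So t = 0.5/0.149 = 3.36 on 13 df, p=0.005.
- Fisher: given one non-responder among 15, chance alone makes that subject one of the two carriers with probability 2/15 = 0.13.
- Barnard's unconditional exact test gives 0.055, Boschloo's 0.11 and Welch's t-test 0.50.

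**Other tables.**

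| Carriers vs non-carriers | Pooled t | Fisher |
|---|---|---|
| 0/1 vs 13/14 | 0.005 | 0.13 |
| 2/3 vs 12/12 | 0.040 | 0.20 |
| 0/2 vs 11/13 | 0.009 | 0.057 |
| 0/2 vs 12/13 | 0.0005 | 0.029 |
| 1/3 vs 12/12 | 0.0005 | 0.029 |
| 0/1 vs 14/14 | zero variance | 0.067 |
| 0/2 vs 13/13 | zero variance | 0.0095 |

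In the fourth, fifth and last rows Fisher's test is also significant, so the tests do not always disagree.

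**Type I error of the pooled t** (all tables enumerated, response rate 50-95%, complete separation counted as rejection):
- 1 carrier: 0.6-9.7%. At 85% response, nearly all of this is a non-responding carrier with at least 12 of 14 others responding: 0.15 × 0.648 = 9.7%.
- 2 carriers: 2.3-5.6%. 3 carriers: 4.4-8.8%.
- Averaged over carrier counts: 2.3-6.0% at 12.5% carriers (2.3-5.4% if separation is not counted), 3.6-5.4% at 20% and 3.4-4.7% at 25%.

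**Disagreement with no true association, 12.5% carriers.** The chance of a finite pooled t with p<0.05 but Fisher p≥0.05 is 1.7%, 3.2%, 4.6%, 4.8% and 3.6% at response rates of 50%, 70%, 80%, 90% and 95%. The single table 1/2 vs 13/13 at 90% has probability 0.289 × (2 × 0.9 × 0.1) × 0.9¹³ = 1.3%.

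**Zero within-group variance with at least one carrier.** The probability is 3%, 19% and 41% at response rates of 80%, 90% and 95%. Complete separation accounts for only 0.3%, 0.7% and 0.7%. The rest is almost entirely tables in which everyone responds.

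**The case against.** The strongest defence is that this is an exploratory comparison in a 15-subject pilot, with no power claim, and that the planned test holds its level on average. Section 7.2.3 also has the proportions themselves reported, so a reader would see the small counts. All of this stands, and it limits the point to a minor one.

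A second objection is that Fisher's test is a harsh comparator. This stands in part. Its size is 0% with one carrier, at most 0.9% with two and at most 1.8% with three, so some of the gap between 0.005 and 0.13 is its conservatism. Even against Barnard's 0.055, though, the t-test p-value is about ten times too small.

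A third objection is that pooling is inferred. If Welch's test were meant, 1/2 vs 13/13 would give 0.50 and the overstatement would reverse. With one carrier Welch's test cannot be computed at all, so that reading does not rescue the plan.

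A reader might infer three stronger things that the documents do not support:
- *That the test grossly inflates false positives.* The average is 2-6%; the excess appears only at particular carrier counts.
- *That the misleading tables are likely.* They arise in about 2-5% of trials under no association.
- *That the test will often fail.* The 19% and 41% figures come almost wholly from trials in which everyone responds, so there is no difference to report. They also need response rates of 90% and 95%. The cited case reports "with 90% of these showing marked improvement" concern a different drug class and are not a PASI 50 rate.

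**Conclusion.** The point holds as a minor error of method. The planned test is unsuited to a yes/no outcome with one to three subjects in a group, which has a 76% chance at the protocol's sporadic rate. A single p-value can be far too small, as 1/2 vs 13/13 shows, and the type I error depends on how many carriers happen to enrol. Complete separation, where the statistic has no finite value although the proportions differ, occurs in under 1% of trials at the response rates checked.

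The conclusion assumes the pooled reading, a carrier rate near "12.5% of individuals with sporadic PRP" and a common response rate of 50-95%. More familial cases would raise the carrier count and ease the problem without removing it. The primary analysis is unaffected.

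**What to change.** Replace the t-test sentence for this comparison in section 7.2.3 with:

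> PASI 50 response by CARD14 status will be reported as responders/total in each group with exact (Clopper-Pearson) 95% confidence intervals and a two-sided Fisher's exact p-value labelled exploratory; if either group is empty, only the observed proportion and interval will be reported.

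The p-value is fixed in advance rather than left optional, and the last clause covers the 13% chance of no carriers. The intervals show how little such data can say: 1-99% for 1/2 and 75-100% for 13/13.

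The cost is one sentence and no new data. The downside is low sensitivity: with one carrier Fisher's p-value cannot go below 1/15 = 0.067, so the result will be mainly descriptive. The same edit could state the visit at which PASI 50 response is judged, since neither section 3.2.4 nor section 7.2.3 gives one for this comparison.

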7. STATISTICAL CONSIDERATIONS

7.1. Sample Size Computation and Power Analysis

This is a pilot study with no published baseline data; thus a power analysis was performed with the following rough assumptions. With measurement of the mean paired difference in PASI score before and after treatment of a minimum of 10 subjects, we would have 80% power at the 0.05 level to detect a mean within-subject change of 8-points when the standard deviation is 8-points. Due to the uncertainty inherent with a pilot study, the goal number of subjects with PRP who will be recruited for the study is 15.

				Mean Change	Standard
Power (1-ß)	Sample Size	а	ß	in PASI	Deviation
0.9998	10	0.05	0.0002	-8	4
0.9940	10	0.05	0.0060	-8	5
0.9621	10	0.05	0.0379	-8	6
0.8942	10	0.05	0.1058	-8	7
0.8031	10	0.05	0.1969	-8	8
0.9873	10	0.05	0.0127	-6	4
0.9203	10	0.05	0.0797	-6	5
0.8031	10	0.05	0.1969	-6	6
0.6755	10	0.05	0.3245	-6	7
0.5620	10	0.05	0.4380	-6	8

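### Section 7.2.3 places its multiplicity adjustment on the comparison with normal and psoriatic tissue; on the plain reading, the paired before/after RNA-Seq and serum cytokine tests have none

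*Combined protocol and SAP*

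**What the plan says.** Section 3.2.4 (Exploratory/Mechanistic Endpoints) sets the assay: "Cutaneous gene expression of the epidermis and dermis will be analyzed by RNA Sequencing". It gives no gene panel, gene count or expression filter. Its list beginning "Upregulation of Th17 cytokines (IL-17A, IL-17F, IL-22) and pro-inflammatory innate cytokines (TNF, IL-6, IL-12, IL-23, IL-1beta) compared to normal skin" reports earlier findings and does not limit what will be tested.

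The skin bullet in section 7.2.3 (Exploratory Endpoint Analyses) covers "The gene expression level from the tissue biopsy, before, 4 weeks, and 24 weeks after treatment". These levels "will be analyzed for statistical significance using a pared, two-tailed Student's t-test and also compared with normal and psoriatic skin", and the test for that last comparison is a "two-sample Student's t-test with unequal variance adjusted for multiple comparisons". The serum cytokine bullet is built the same way.

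Nothing else in section 7 adjusts the paired tests. The plan names no adjustment method, family of tests, significance threshold for exploratory analyses, normalization or RNA-Seq model.

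**The concern.** The adjustment phrase closes the clause about normal and psoriatic tissue, and the paired clause before it has none. Yet the paired contrasts, week 0 against week 4 and week 0 against week 24, show most directly how guselkumab alters skin and serum, which is the exploratory objective in section 2.3. The plan tests them for statistical significance, so they are not purely descriptive.

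RNA-Seq without a panel can mean thousands of tests per contrast. Unadjusted, the list of genes said to change under treatment could hold many that did not, and the plan would give no control over that share.

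A secondary matter is the per-gene Student's t-test. With 10 to 15 pairs, each gene's variance is estimated on only 9 to 14 degrees of freedom. That costs power once the false discovery rate is controlled.

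**Working it through.** **Inputs from the plan.** Pairs: a minimum of 10 and a recruitment goal of 15 (section 7.1). Contrasts: two changes from baseline (section 7.2.3).

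**Assumptions, not in the plan.** Exploratory threshold 0.05 two-sided (section 7.1 gives 0.05 only for the primary power calculation); 10,000 to 20,000 genes tested one by one; true changes of 1 SD of the paired difference; 10%, 20% or 50% of genes truly changing.

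**1. The plan's own figure.** Section 7.1 says "we would have 80% power at the 0.05 level to detect a mean within-subject change of 8-points when the standard deviation is 8-points" with 10 subjects. A two-sided paired t-test with 9 degrees of freedom and noncentrality (8/8) × √10 = 3.162 has power 0.8031, matching the table; the other nine rows agree within 0.0001. The figure concerns PASI. It also equals the power of one unadjusted gene test for a 1 SD change with 10 pairs.

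**2. Expected false calls per contrast** = genes × share unchanged × 0.05.

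| Genes | None change | Half change |
|---|---|---|
| 10,000 | 10,000 × 1 × 0.05 = 500 | 10,000 × 0.5 × 0.05 = 250 |
| 20,000 | 20,000 × 1 × 0.05 = 1,000 | 20,000 × 0.5 × 0.05 = 500 |

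Two contrasts double these. A simulation of 15,000 correlated genes, none changing, averaged about 750 false calls (15,000 × 0.05 = 750), with a 95% range of roughly 600 to 930. With Benjamini-Hochberg at 5% the mean was under 0.1.

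The count depends on how many genes are tested: 2,000 unchanged genes give 2,000 × 0.05 = 100 per contrast. The eight cytokines named in section 3.2.4 alone would give 8 × 0.05 = 0.4.

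**3. False share of called genes**, 12 pairs. Power per gene for a 1 SD change (11 degrees of freedom, noncentrality √12 = 3.464) is 0.8829. For 15,000 genes:

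| Share changing | False calls | True calls | False share |
|---|---|---|---|
| 10% | 13,500 × 0.05 = 675 | 1,500 × 0.8829 = 1,324 | 675/1,999 = 34% |
| 20% | 12,000 × 0.05 = 600 | 3,000 × 0.8829 = 2,649 | 600/3,249 = 18% |
| 50% | 7,500 × 0.05 = 375 | 7,500 × 0.8829 = 6,622 | 375/6,997 = 5% |

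The share does not depend on the number of genes. In the 10% case it is 36% with 10 pairs and 32% with 15, so reaching the recruitment goal does not remove it.

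**4. With Benjamini-Hochberg at 5%**, the expected false share is at most about 5%. Simulation gave 4 to 5% in the 10% case with 12 pairs (26 false of 553 calls) and about 4% in the 20% case with 10 or 15 pairs.

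**5. What FDR control costs**, 15,000 genes, 10% changing, 12 pairs:

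- Unadjusted paired t-tests find about 1,315 of 1,492 true changes (88%).
- Paired t-tests with Benjamini-Hochberg find about 527 (35%).
- A moderated t-test with Benjamini-Hochberg finds about 710 of 1,491 (48%), assuming a prior worth 4 degrees of freedom.

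With 15 pairs the gain from moderation is smaller: about 1,062 true changes found against 968. Bonferroni would be impractical: at 15,000 genes and 15 pairs, power for a 1 SD change is about 2%.

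**The case against.** The strongest reply is that the sentence describes two tests and that its closing phrase, with no comma before it, may be meant to govern both. Both mechanistic bullets show that the sponsor had multiplicity in mind. This stands as a possible reading. A reader might infer that the sponsor decided to leave the paired tests unadjusted, or that hundreds of false genes will be published; the text supports neither. Even on the generous reading, the method and family are unnamed.

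The skin endpoint is normalization, to which the comparison with normal skin is directly relevant, and that comparison is adjusted. This is true, but the paired tests still serve the objective in section 2.3 and the serum endpoint, which is a change in cytokine levels.

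The share of genes changing is unknown. Effective treatment of widespread inflamed skin could change many, and the unadjusted false share would then be small. This stands, which is why a range is given.

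A reader might also infer that the t-test is invalid for RNA-Seq, or less powerful than a count model as the plan stands. Neither follows. The plan speaks of expression level, and normalized log values can be analyzed with a paired t-test. Unadjusted t-tests find more true changes than any of the FDR-controlled options in step 5; moderation gains power only when both methods control the FDR.

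Finally, this is exploratory work in an open-label pilot of 15 subjects. That limits the weight of the point. It does not explain why one set of tests should be adjusted and the other not.

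**Conclusion.** The concern holds on the plain reading of section 7.2.3, and on the other reading the plan still needs clarifying. If the paired gene tests are run unadjusted, expect about 250 to 1,000 false calls per contrast, and a false share of about 5% to 34% with 12 pairs and 1 SD changes, against at most about 5% with Benjamini-Hochberg.

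These sizes rest on the assumed gene count, the 0.05 threshold, gene-by-gene testing, the effect size and the share of genes changing. The false-call counts would be far smaller if testing were limited to well under about 2,000 genes, but no such limit is stated.

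The gene counts do not carry over to serum. The same gap exists there, but its size depends on the number of cytokines in the multiplexed panel, which the plan does not give. The primary PASI analysis is unaffected.

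**What to change.** In section 7.2.3:

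- State that the paired gene tests are controlled at 5% FDR by Benjamini-Hochberg across genes, and define the family: which contrasts, and whether epidermis and dermis are pooled or handled separately.
- Apply the same control to the paired serum cytokine tests, and state the panel size.
- Replace the per-gene Student's t-test with a moderated model that has subject as a blocking factor and week as a factor, for example limma-voom. This keeps the pairing and recovers some of the power that FDR control costs at 10 to 15 pairs.

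The change needs SAP wording and free software, with no new data or visits. The scientific cost is a shorter gene list with some true changes missed, and the report should say so.

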8. SAFETY

8.1. Specification of Safety Parameters

As the sponsor of the Study, OHSU and the PI shall be solely responsible for complying, within the required timelines, any safety reporting obligation to competent Health Authorities, IRB and any participating (co or sub) investigators, as defined in applicable laws and regulations. For the purposes of this protocol, safety data includes adverse events, product quality complaints (PQCs), and special situations including pregnancies. Safety assessments will be based on medical review of adverse events and the results of safety evaluations at specified time points as described in Section 5.1 Study Visit Procedures. Any clinically significant adverse events persisting at the end of treatment visit will be followed by the Investigator until resolution/stabilization or death, whichever comes first.

OHSU and the PI will provide safety information to Janssen Scientific Affairs on adverse events, special situations including pregnancies and product quality complaints as defined within this protocol.

This Study has been designated as an interventional study. As such, all adverse events for Janssen Study drugs regardless of causality and special situations excluding those from subjects not exposed to a Janssen Study drug and product quality complaints with or without an adverse event as described in this Protocol will be reported from the time a subject has signed and dated an Informed Consent Form (ICF) until completion of the subject's last study-related procedure (which may include contact for follow-up safety). Serious adverse events will be reported up to week-36 (16 weeks after the last dose of study drug).

